8.2 Safety assessments

Planned time points for all safety assessments are provided in Table 1. Notably, clinical chemistry, haematology, urinalysis, physical examination, vital signs, height and weight, ECG, echocardiogram, ophthalmologic assessment, Tanner stages and performance status will be assessed at screening, at the end of each cycle up to the end of Cycle 4, every 2 cycles up to the end of Cycle 12, every 4 cycles up to the end of Cycle 24, and every 6 cycles thereafter, as long as the subject remains on study treatment. Pregnancy tests will be performed at the end of each cycle. An x-ray will be performed at screening and at other visits/cycles, if clinically indicated. Safety assessments will also be performed at other visits during Cycles 0 and 1, as detailed in Table 1.

8.2.1 Clinical safety laboratory assessments

See Table 10 for the list of clinical safety laboratory tests to be performed and Table 1 for their timing and frequency. All protocol-required laboratory assessments, as defined in the table, must be conducted in accordance with the laboratory manual and Table 1. The blood sample for clinical chemistry should be collected under fasting status. The investigator should make an assessment of the available results with regard to clinically relevant abnormalities. The laboratory results should be signed and dated and retained at the centre as source data for laboratory variables. For information on how AEs based on laboratory tests should be recorded and reported, see Section 8.3.7.

Additional safety samples may be collected if clinically indicated at the discretion of the investigator. The date, time of collection and results (values, units and reference ranges) will be recorded on the appropriate eCRF.

Clinical chemistry, haematology and urinalysis assessments will be performed at a local laboratory at or near to the investigator site. Sample tubes and sample sizes may vary depending on the laboratory method used and routine practice at the site.

Haematology/Haemostasis (whole blood)	Clinical chemistry (serum or plasma)
B – Erythrocyte count	S/P – Albumin
B – Haemoglobin	S/P – Alkaline phosphatase
B – Platelet count	S/P – Alanine aminotransferase
B – Leukocyte count	S/P – Aspartate aminotransferase
B – Leukocyte differential count (absolute count)	S/P – Total calcium
B – Neutrophil count	S/P – Creatinine
B – Eosinophil count	S/P – Gamma-glutamyl transferase
B – Basophil count	S/P – Magnesium
B – Lymphocyte count	S/P – Phosphate
B – Monocyte count	S/P – Potassium
	S/P – Sodium
Urinalysis (dipstick)	S/P – Total protein
U – Glucose	S/P – Total bilirubin
U – Protein/albumin	S/P – Urea nitrogen ^a
U - Haemoglobin/erythrocytes/blood/ Leucocytes	S/P – Uric acid
	S/P – Creatine kinase ^b
	S/P – Amylase
	S/P – Troponin (isoform per site norm) ^c

Table 10Laboratory safety variables

B=blood; CK=creatine kinase; LLN=lower limit of detection; LVEF=left ventricular ejection fraction; P=plasma; S=serum; U=urine.

^a Urea or blood urea nitrogen based on local site practice.

^b CK to be assessed at screening and if clinically indicated (e.g. muscle symptoms).

^c Troponin (isoform per site norm), should be assessed at screening, and performed when there is a significant drop in LVEF (of ≥10 percentage points relative to baseline and to an absolute LVEF below the institution's LLN on study treatment) or for any cardiorespiratory events with no obvious diagnosis. If troponin assessments are not available, per local practice, CK-MB isoform should be assessed. Subjects should be managed according to the algorithm provided in Appendix E.

Clinical chemistry, haematology and urinalysis testing will be repeated as clinically indicated as part of the routine management of the subject on the occurrence of AEs.

Urine microscopy will be assessed if other urinalysis measurements are abnormal or if clinically indicated.

If unexplained muscle weakness or myalgia (muscle pain) occurs, the subject should have a neuromuscular examination, urine analysis and CK measurement performed (with an additional CK-MM isoform measurement where possible) and be managed according to local practice.

All subjects with an AST, ALT or bilirubin value $\geq 1.5 \times ULN$ at time of the last dose of selumetinib should have a further liver chemistry profile (AST, ALT, bilirubin and alkaline phosphatase [ALP]) performed 30 days (± 7 days) after permanent discontinuation of selumetinib.

N.B. In the case of a subject showing an AST or $ALT \ge 3 \times ULN$ together with total bilirubin $\ge 2 \times ULN$, please refer to Appendix D 'Actions required in cases of increases in liver biochemistry and evaluation of Hy's Law' (HL), for further instructions.

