2.3 Benefit/risk assessment

2.3.1 Overall benefit/risk assessment

The primary objective of the study is to assess the safety, tolerability and PK of selumetinib in Chinese paediatric and adult subjects with NF1 and inoperable PN. As identified in the SPRINT study, selumetinib at a dose of 25 mg/m² had promising clinical activity for the treatment of NF1 and inoperable PN. In the phase I portion of the study, ORR was 66.7% (16/24 patients). The response rate was confirmed in SPRINT Phase II Stratum 1, in which the overall response rate by NCI POB central analysis was 66% (95% CI: 51.2, 78.8; 33/50 patients). Furthermore, responses were generally durable (median DoR based on NCI POB central analysis was not reached) and there was evidence of clinical benefit including improvement in pain and motor function. Selumetinib may therefore offer the potential for direct benefit in Chinese paediatric and adult subjects with NF1 and inoperable PN in terms of disease stabilisation or shrinkage, a reduction in tumour symptoms including pain, and improvements in health-related quality of life (HRQoL) and function. The primary risk to subjects participating in this study is from toxicity of selumetinib, an investigational agent. In the SPRINT study the most frequent adverse events (AEs; any grade) considered by the investigator to be possibly related to selumetinib at any dose in subjects with NF1 and inoperable PN included acneiform rash, asymptomatic creatine kinase (CK) elevation, and CONFIDENTIAL AND PROPRIETARY 29 of 183

gastrointestinal effects (abdominal pain, diarrhoea, nausea, and vomiting). AEs were predominantly mild/moderate in severity, predictable and manageable with standard clinical practice and generally did not affect the ability of subjects to remain on treatment.

The proposed exclusion criteria, safety monitoring, starting dose, toxicity management guidance and stopping criteria will minimise the risks for the subjects participating in this study. Additionally, AEs will be carefully monitored throughout the study.

The benefit/risk assessment for this study therefore appears to be acceptable for subjects for whom there is no alternative standard therapy.

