3. OBJECTIVES AND ENDPOINTS

Table 2Study objectives

Primary objectives:	Endpoints:	
To assess the safety and tolerability of selumetinib in Chinese paediatric and adult subjects with NF1 and inoperable PN	 Paediatric and adult cohorts: Safety and tolerability will be evaluated in terms of AEs, clinical safety laboratory assessments, physical examination, vital signs, height/weight, ECG, echocardiogram, ophthalmologic assessment and performance status. Paediatric only: Safety and tolerability will also be evaluated in terms of bone growth and Tanner stages. 	
	Assessments related to AEs will include:	
	Occurrence/frequency.	
	• Relationship to IP as assessed by investigator.	
	CTCAE grade.	
	• Seriousness.	
	• Death.	
	• AEs leading to discontinuation of IP.	
	• AEs of special interest.	
To characterise the PK of selumetinib and its metabolite (N-desmethyl selumetinib) in Chinese paediatric and adult subjects with	PK parameters for selumetinib and N-desmethyl selumetinib will be derived following single dose and multiple doses. These may include, but are not limited to:	
NF1 and inoperable PN	After a single dose:	
	• AUC.	
	• AUC ₀₋₁₂ .	
	• AUC _{0-t} .	
	• C _{max} .	
	• t _{max} .	
	• t _{1/2} .	
	After multiple doses:	
	• AUC _{0-12,ss} .	
	• C _{max,ss} .	
	• Rac.	

Secondary objectives:	Endpoints:	
To evaluate the clinical efficacy of selumetinib in Chinese paediatric and adult subjects with NF1 and inoperable PN on ORR, DoR, PFS, TTP, and TTR	ORR is defined as the proportion of subjects who have a complete response or confirmed partial response (defined as a target PN volume decrease ≥20% compared to baseline, confirmed by a consecutive scan within 3 to 6 months after first response, as determined by the investigator and independent central review per Response Evaluation in Neurofibromatosis and Schwannomatosis (REiNS) criteria.	
	DoR is defined as the time from the date of first documented response (which is subsequently confirmed) until the date of documented progression or death in the absence of disease progression, as determined by the investigator and independent central review per REiNS criteria.	

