8.3.11 Adverse events of special interest

Adverse events of special interest are events of scientific and medical interest specific to the further understanding of selumetinib safety profile and require close monitoring and rapid communication by the investigators to AstraZeneca. An AESI can be serious or non-serious. All AESI should be recorded in the eCRF as soon as possible, and preferably within 24 hours of occurrence. Serious AESIs will be recorded and reported as per Section 8.4.1. Adverse events of special interest based on examinations and tests should be reported in accordance with Section 8.3.7. Adverse events of special interest are shown in Table 11.

AESI	MedDRA Preferred Terms (PT) Defining the AESIs
Ocular toxicity	Chorioretinopathy (central serous retinopathy [CSR]); Retinal detachment; Retinal tear; Vision blurred; Visual impairment; Vitreous floaters; Photopsia; Eye disorder; Photophobia; Retinal vein occlusion (RVO); Detachment of retinal pigment epithelium (Retinal pigment epithelial detachment [RPED]).
Hepatotoxicity	Drug-induced liver injury; ALT increased; AST increased.
Muscular toxicity	Blood creatine phosphokinase increased; Musculoskeletal pain; Muscular weakness; Myalgia; Rhabdomyolysis; Myoglobin blood increased; Myoglobin urine present; Acute kidney injury; Myopathy.
Cardiac toxicity	Ejection fraction decreased; Oedema peripheral; Peripheral swelling; Oedema; Left ventricular dysfunction; Ventricular dysfunction.

Table 11Adverse Events of Special Interest

CONFIDENTIAL AND PROPRIETARY

AESI	MedDRA Preferred Terms (PT) Defining the AESIs
For Paediatric population only	
Physeal dysplasia	Metaphyseal dysplasia, Multiple epiphyseal dysplasia, Arthralgia, Joint stiffness, Joint hyperextension, Gait disturbance, Short stature.
Choking on the capsule	Choking, Retching.

AE=adverse event; MedDRA=Medical Dictionary for Regulatory Activities.

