9.5.2 Safety analyses

Safety analyses will be performed using the safety analysis set.

AEs will be coded using the most recent version of the Medical Dictionary for Regulatory Activities that will have been released for use by AstraZeneca/designee.

Safety data will be presented by using descriptive statistics and by cohort unless otherwise specified.

AEs will be presented for each cohort by System Organ Class and/or Preferred Term covering the number and percentage of subjects reporting at least 1 event and the number of events where appropriate.

AEs occurring prior to the start of IP and treatment-emergent AEs will be presented separately.

An overview of AEs will be presented for each cohort. The number and percentage of subjects with any AE, AEs with outcome of death, SAEs, AEs leading to discontinuation of IP, AEs leading to IP dose interruptions, AEs leading to IP dose reduction and AEs leading to

withdrawal from study, as well as the number of individual occurrences in those categories, will be presented.

Separate AE tables will be provided taking into consideration causal relationship as assessed by the investigator, CTCAE grading, seriousness, death and events leading to discontinuation of IP as well as other actions taken related to IP, AEs of special interest, and other significant AEs.

An additional table will present the number and percentage of subjects with the most common AEs (frequency of >10%).

Key subject information will be presented for subjects with AEs with an outcome of death, SAEs, and AEs leading to discontinuation of IP.

An AE listing for the safety analysis set will cover details for each individual AE.

Full details of AE analyses will be provided in the SAP.

The following events are considered to be treatment-emergent:

- AEs with an onset date on or after the first dose of IP and within 30 days after the last dose of IP.
- Worsening of pre-existing events on or after the first dose of IP and within 30 days after last dose of IP.

Laboratory data (haematology, clinical chemistry and quantitative urinalysis) will be summarised using descriptive statistics over time in terms of absolute values and changes from baseline. Shift tables showing CTCAE grade changes from baseline on treatment will be produced by laboratory parameter for haematology and clinical chemistry.

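### No on-treatment CK is scheduled, so asymptomatic CK rises, a named frequent effect of selumetinib, will be under-counted and any CK shift table will rest on selectively tested subjects

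*Protocol*

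**What the plan says.** Table 10 in Protocol Section 8.2.1 lists CK under clinical chemistry, but footnote b takes it off the visit schedule: "CK to be assessed at screening and if clinically indicated (e.g. muscle symptoms"). The only specific trigger spelled out is muscular. The same section says: "If unexplained muscle weakness or myalgia (muscle pain) occurs, the subject should have a neuromuscular examination, urine analysis and CK measurement performed". Section 2.3.2 gives the same trigger.

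Other parts of the protocol treat CK as an effect to be measured:

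- Section 2.3.1 says the most frequent related adverse events in the earlier paediatric study (SPRINT) "included acneiform rash, asymptomatic creatine kinase (CK) elevation".
- Section 2.3.2 says that regular monitoring of muscle symptoms, and specific tests that include blood CK, are built in so that problems are identified promptly.
- Section 8.3.11, Table 11, defines the muscular-toxicity event of special interest by a list that begins "Blood creatine phosphokinase increased; Musculoskeletal pain; Muscular weakness; Myalgia; Rhabdomyolysis".
- Appendix E 2, Table 16, grades a CPK increase purely by multiples of the upper limit of normal.
- Section 9.5.2 promises: "Shift tables showing CTCAE grade changes from baseline on treatment will be produced by laboratory parameter for haematology and clinical chemistry".
- Section 3, Table 2, puts this within a primary objective: "Safety and tolerability will be evaluated in terms of AEs, clinical safety laboratory assessments, physical examination, vital signs", with events of special interest listed among the adverse event assessments.

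**The concern.** The effect the protocol names is a CK rise without symptoms. The testing rule waits mainly for symptoms. A subject with the named effect and nothing else gives no prompt for the test, so the plan undercounts an effect it already expects.

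This is not something a statistical analysis plan can repair. It can decide how sparse CK values are displayed, but it cannot recover values that were never measured. At stake are the reported frequency of asymptomatic CK elevation in each cohort and the meaning of any CK shift table. Section 2.1 says the paediatric cohort exists to supply Chinese safety data for registration, so undercounting a known frequent effect matters there.

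**Working it through.** The protocol states no CK rate and bases no calculation on one, so there is no figure to reproduce.

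**Step 1. Count the scheduled tests.** Section 1.1, Table 1 and its footnote j place on-treatment chemistry at Cycle 1 Day 8, then at the ends of Cycles 1, 2, 3, 4, 6, 8, 10, 12, 16, 20 and 24.

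| Up to | Routine chemistry draws | Mandated CK |
|---|---|---|
| Interim analysis (end of Cycle 4) | 1 + 4 = 5 | 0 |
| Primary data cut-off (end of Cycle 10) | 5 + 3 = 8 | 0 |
| Final data cut-off (end of Cycle 24) | 8 + 4 = 12 | 0 |

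Troponin has its own event-driven footnote and is not part of this count.

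**Step 2. Relate detection to occurrence.** Let p be the true proportion of subjects with a CK rise on treatment, s the share of those rises that happen to be tested, and n = 16 per cohort (Section 9.2). Expected rises are n × p and expected detected rises are n × p × s. The fraction missed is 1 − s whatever p is, so there is under-counting for every s below 1.

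**Step 3. Illustrate the range.** Neither p nor s is in the protocol; both are assumptions.

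| p | Expected rises, 16p | Seen, s = 0 | s = 0.10 | s = 0.25 | s = 0.50 |
|---|---|---|---|---|---|
| 0.3 | 4.8 | 0 | 0.5 | 1.2 | 2.4 |
| 0.5 | 8.0 | 0 | 0.8 | 2.0 | 4.0 |
| 0.7 | 11.2 | 0 | 1.1 | 2.8 | 5.6 |

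Section 9.5.2 also plans a table of common adverse events, those above 10%. With 16 subjects this needs at least 2 (1/16 = 6.25%, 2/16 = 12.5%). With q = p × s, the chance that at least 2 rises are detected is 1 − (1 − q)^16 − 16q(1 − q)^15. At s = 0.10 this is 0.08, 0.19 and 0.31 for p = 0.3, 0.5 and 0.7. These are ceilings for that table, because a detected rise must still qualify as an adverse event.

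**Step 4. Apply the reporting filter.** Section 8.3.11 sends test-based events of special interest to Section 8.3.7. There, a deterioration in a mandated laboratory value becomes an adverse event only if it meets serious criteria, leads to discontinuation of treatment, or is judged clinically relevant. The counts in Step 3 are therefore laboratory rises, not events of special interest.

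**Step 5. Look at the shift table.** Every subject has a screening CK, but only those tested for cause have an on-treatment value. Any CK shift table thus describes a subset chosen for reasons related to the outcome. Shift tables do not pass through the Section 8.3.7 filter, so this holds however events are reported.

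**The case against.** The symptom trigger appears in both Section 2.3.2 and Section 8.2.1, so it looks deliberate. The wording is also wider than symptoms: testing is allowed whenever clinically indicated, investigators may draw further safety samples, and chemistry is repeated as indicated when adverse events occur. That stands, and it limits the claim to under-ascertainment. A reader might infer that the primary safety endpoint cannot see CK rises at all. The documents do not support this, because an incidental CK result would be recorded. But discretionary testing is selective testing, which is where the bias arises.

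Four other inferences go too far:

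- That CK incidence will be biased low against SPRINT. The protocol gives no CK schedule or reporting rule for that study and plans no formal comparison with it.
- That the 30% to 70% range measures lost events of special interest. It is an assumed laboratory rate, and Section 8.3.7 would filter it even if CK were drawn at every visit.
- That no statement on muscular safety is possible. Table 11 lists other muscular terms, such as myalgia, muscular weakness and rhabdomyolysis, and symptomatic events are still sought by open questioning. CK is one analyte in a multi-domain safety endpoint.
- That a CK shift table will overstate elevations. The direction depends on whether percentages are taken over tested subjects or over the whole cohort, and the protocol does not say.

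A last objection is that scheduled CK is not free of consequences. Section 6.6 attaches dose actions to related grade 3 and grade 4 events unless Appendix E says otherwise, and Table 16 sets those CPK grades by value alone (above 5 and above 10 times the upper limit). The E 2 algorithm does not appear in the text available, so its effect cannot be checked. This stands as a real cost.

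**Conclusion.** The point holds as an inconsistency between what the protocol expects and what it measures. It schedules no on-treatment CK against 12 routine chemistry draws, while naming asymptomatic CK elevation as frequent, listing "Blood creatine phosphokinase increased" as a term of special interest and planning shift tables for clinical chemistry. Asymptomatic CK rises will be under-ascertained, and any CK shift table will rest on a selectively tested subset.

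The direction of the under-count needs only that some rises go untested. Its size is unknown: the figures in the working rest on assumed values of p and s and refer to laboratory rises. The change should be made, but the gap is confined to asymptomatic CK elevation.

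**What to change.** Reconcile Sections 2.3.1, 2.3.2, 8.2.1 (Table 10 footnote b), 8.3.11, 9.5.2 and Appendix E 2. The sponsor should choose one of two routes.

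1. **Report CK from the chemistry samples already scheduled in Table 1**, keeping extra tests when clinically indicated. This adds one analyte to blood already drawn, plus edits to footnote b and the laboratory manual. It will produce more asymptomatic graded values, and the sponsor must confirm how these are handled under Section 6.6 and Appendix E 2 before the change takes effect. Visits completed before the change would still lack CK, and the report should say so.
2. **Keep footnote b**, exclude CK from the shift tables, reword the Section 2.3.2 statement on CK monitoring to match, and state in the report that asymptomatic CK elevation is under-ascertained and its incidence cannot be estimated from this trial. This costs only text, but leaves the question unanswered.

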8.2.1.1 Pregnancy test

Pregnancy tests (blood or urine tests are acceptable based on the site's standard clinical practice) should be performed for women of childbearing potential only (see Section 5.1). Pregnancy testing will be performed at screening, Cycle 0 Day 1 and at the end of each cycle in women of childbearing potential only (see Section 5.1 for details) and more frequently, if clinically indicated as outlined in Table 1.

8.2.2 Physical examinations

A complete physical examination will be performed and will include an assessment of the following: general appearance, respiratory, cardiovascular, abdomen, skin, head and neck (including ears, eyes, nose and throat), lymph nodes, thyroid, musculoskeletal (including spine and extremities) and neurological systems.

Physical examination will be performed at the times specified in Table 1. Investigators should pay special attention to clinical signs related to previous serious illnesses. New or worsening abnormalities may qualify as AEs (see Section 8.3.7).

8.2.3 Vital signs

Axillary temperature, pulse rate, oxygen saturation by pulse oximetry, respiratory rate, and BP will be assessed in accordance with Table 1 and additionally at the discretion of the investigator if clinically indicated.

Vital signs will be taken prior to blood collection.

Blood pressure and pulse measurements will be assessed in a sitting position and preceded by at least 5 minutes of rest in a quiet setting without distractions (e.g. television, cell phones). Manual techniques will be used only if automated devices are not available.

8.2.4 Height and weight

Height and weight will be measured at the times outlined in Table 1. The subject's height will be recorded in centimetres (cm) and weight will be recorded in kilograms (kg). Height and weight measurements will be performed in light clothing and with shoes off. CONFIDENTIAL AND PROPRIETARY 72 of 183
For paediatric subjects:

Collect all available documented previous height and weight measurements and growth curves if available at screening.

Height: The subjects should take off shoes and socks, and heels should be placed against a wall with ankles together. Height should be measured in a standing position with a stadiometer. Height measurements should be taken at approximately the same time of day for each visit, when possible. The height should be plotted on a standardised growth chart. In subjects with known leg length discrepancy due to limb hypertrophy, height should be measured with the subject bearing weight on the limb without hypertrophy.

